12.5 Appendix 5: Contraceptive Guidance and Collection of Pregnancy Information

Definitions

Woman of Childbearing Potential (WOCBP)

A woman is considered fertile following menarche and until becoming postmenopausal unless permanently sterile (see below).

[figure not shown]
Women in the following categories are not considered WOCBP:

1. Premenarchal
2. Premenopausal female with 1 of the following:
 - Documented hysterectomy
 - Documented bilateral salpingectomy
 - Documented bilateral oophorectomy

[figure not shown]
Note: Documentation can come from the site personnel's: review of the participant's medical records, medical examination, or medical history interview.

3. Postmenopausal female
 - A postmenopausal state is defined as no menses for 12 months without an alternative medical cause. A high follicle-stimulating hormone (FSH) level in the postmenopausal range may be used to confirm a postmenopausal state in women not using hormonal contraception or hormonal replacement therapy (HRT). However, in the absence of 12 months of amenorrhea, a single FSH measurement is insufficient.
 - Females on HRT and whose menopausal status is in doubt will be required to use one of the non-hormonal highly effective contraception methods if they wish to continue their HRT during the study. Otherwise, they must discontinue HRT to allow confirmation of postmenopausal status before study enrollment.

[figure not shown]
Contraception Guidance

Approval Date: 12-Feb-2021 17:35:16 (GMT)

Approval Date: 12-Feb-2021 17:35:16 (GMT)

Approval Date: 12-Feb-2021 17:35:16 (GMT)

12.6 Appendix 6: Liver Safety: Suggested Actions and Follow-up Assessments

Hy's law cases are considered AESIs. Hy's Law criteria are as follows:

- Alanine aminotransferase (ALT) or aspartate aminotransferase (AST) $\geq 3 \times$ upper limits of normal (ULN)
- AND Total bilirubin $\geq 2 \times$ ULN
- AND Alkaline phosphatase $< 2 \times$ ULN

Investigational product must be discontinued if any of the following criteria are met:

- ALT or AST $\geq 3 \times$ ULN and the participant is symptomatic with the appearance of fatigue, nausea, vomiting, right upper quadrant pain or tenderness, fever, rash, or eosinophilia ($> 5\%$)
- ALT or AST $\geq 3 \times$ ULN and total bilirubin $> 2 \times$ ULN or INR $> 1.5 \times$ ULN
- ALT or AST $\geq 5 \times$ ULN for more than 2 weeks
- ALT or AST $\geq 8 \times$ ULN

The participant may be re-challenged with study treatment only after consultation with the Allergan MSP. For participants who are not re-challenged with study treatment, the participant should be discontinued from the study and complete the Early Termination Visit. Participants should receive appropriate follow-up as per standard of care.

Hy's Law Cases

Sites must report every subject who meets the following Hy's law criteria if this occurs within the time the subject signs the ICF until 30 days after the last dose of study treatment.

A laboratory alert for Hy's laws cases will be in place, and the investigators and Allergan will be notified immediately when the above criteria have been met. Any Hy's laws case should be considered an SAE and also reported as an AE of Special Interest.

Every effort to determine the cause of the liver abnormalities must be made, and close monitoring should be initiated in conjunction with the Allergan medical monitor and in accordance with the FDA "[Guidance for Industry: Drug Induced Liver Injury - Pre-Marketing Clinical Evaluation](#)" July 2009.

12.7 Appendix 7: Medical Device Incidents: Definition and Procedures for Recording, Evaluating, Follow-up, and Reporting

Definitions of a Medical Device Incident

The detection and documentation procedures described in this protocol apply to all sponsor medical devices provided for use in the study (see Section 7.1 for the list of sponsor medical devices).

Medical Device Incident Definition

- A medical device incident is any malfunction or deterioration in the characteristics and/or performance of a device as well as any inadequacy in the labelling or the instructions for use which, directly or indirectly, might lead to or might have led to the death of a participant/user/other person or to a serious deterioration in his/her state of health.
- Not all incidents lead to death or serious deterioration in health. The non-occurrence of such a result might have been due to other fortunate circumstances or to the intervention of health care personnel.

It is sufficient that:

- An **incident** associated with a device happened
- AND
- The **incident** was such that, if it occurred again, might lead to death or a serious deterioration in health.

[figure not shown]
A serious deterioration in state of health can include any of the following:

- Life-threatening illness
- Permanent impairment of body function or permanent damage to body structure
- Condition necessitating medical or surgical intervention to prevent one of the above
- Fetal distress, fetal death, or any congenital abnormality or birth defects

Examples of Incidents

- A participant, user, caregiver, or healthcare professional is injured as a result of a medical device failure or its misuse.
- A participant's study treatment is interrupted or compromised by a medical device failure.
- A misdiagnosis due to medical device failure leads to inappropriate treatment.
- A participant's health deteriorates due to medical device failure.

Documenting Medical Device Incidents

12.8 Appendix 8: Standard Discontinuation Criteria

[figure not shown]
CDISC Submission Value	CDISC Definition
Adverse event	Any untoward medical occurrence in a patient or clinical investigation participant administered a pharmaceutical product and which does not necessarily have a causal relationship with this treatment. An adverse event (AE) can therefore be any unintended sign (including an abnormal laboratory finding), symptom, or disease temporally associated with the use of a medicinal (investigational) product, whether or not related to the medicinal (investigational) product. For further information, see the ICH Guideline for Clinical Safety Data Management: Definitions and Standards for Expedited Reporting. [Modified from ICH E2A] Synonyms: side effect, adverse experience. See also serious adverse event, serious adverse experience. (CDISC glossary)
Completed	To possess every necessary or normal part or component or step; having come or been brought to a conclusion (NCI)
Death	The absence of life or state of being dead (NCI)
Failure to meet randomization criteria	An indication that the subject has been unable to fulfill/satisfy the criteria required for assignment into a randomized group
Lack of efficacy	The lack of expected or desired effect related to a therapy (NCI)
Lost to follow-up	The loss or lack of continuation of a subject to follow-up
Other	Different than the one(s) previously specified or mentioned (NCI)
Investigator decision	A position, opinion or judgment reached after consideration by a physician with reference to subject (NCI)
Pregnancy	Pregnancy is the state or condition of having a developing embryo or fetus in the body (uterus), after union of an ovum and spermatozoon, during the period from conception to birth. (NCI)
Protocol deviation	An event or decision that stands in contrast to the guidelines set out by the protocol (NCI)
Screen failure	The potential subject who does not meet one or more criteria required for participation in a study
Site terminated by sponsor	An indication that a clinical study was stopped at a particular site by its sponsor (NCI)
Study terminated by sponsor	An indication that a clinical study was stopped by its sponsor (NCI)
Withdrawal by participant	An indication that a study participant has removed itself from the study (NCI)

[figure not shown]
12.9 Appendix 9: Study Tabular Summary

Parameter Group	Parameter	Value
Study information	Study Title	A 52-week, Randomized, Double-blind, Placebo-controlled, Phase 3 Study to Evaluate the Safety and Efficacy of Relamorelin in Patients with Gastroparesis
	Clinical Study Sponsor	Allergan Sales
	Study Phase Classification	Phase 3 Study
	Study Indication	Diabetic gastroparesis
	Study Indication Type	Treatment
	Study Type	Efficacy Safety
	Study Length	Up to 58 weeks, consisting of a 4-week Screening Period, 2-week Run-in Period, and a 52-week Treatment Period
	Planned Country of Investigational Sites	Global
	Planned Number of Subjects	Approximately 5000 participants will be screened in studies RLM-MD-01 and RLM-MD-02. Participants who screen fail those studies for certain reasons (see below) may enter this study to achieve 600 participants assigned to study treatment (400 to relamorelin and 200 to placebo). A total of 300 participants are expected to complete the study (200 relamorelin- and 100 placebo-treated participants).
	FDA-Regulated Device Study Indicator	No
	FDA-Regulated Drug Study Indicator	No
	Pediatric Study Indicator	No
Subject information	Diagnosis Group	Diabetes mellitus
	Healthy Subject Indicator	No
	Planned Minimum Age of Subjects	18
	Planned Maximum Age of Subjects	none
	Sex of Participants	Both
	Stable Disease Minimum Duration	3 months

[figure not shown]
Approval Date: 12-Feb-2021 17:35:16 (GMT)

Parameter Group	Parameter	Value
Treatments	Investigational Therapy or Treatment	relamorelin
	Intervention Type	drug
	Pharmacological Class of Invest. Therapy	synthetic ghrelin analogue
	Dose per Administration	10 µg
	Dose Units	Pre-Filled Cartridge in Multi-dose Pen Injector
	Dosing Frequency	twice daily
	Route of Administration	subcutaneous injection
	Current Therapy or Treatment	treatment
	Added on to Existing Treatments	No
	Control Type	Placebo
	Comparative Treatment Name	none
Study design	Study Type	Interventional
	Intervention Model	Parallel
	Planned Number of Arms	2
	Study is Randomized	yes
	Randomization Quotient	2 : 1
	Study Blinding Schema	Double-blind
	Stratification Factor	Not applicable
	Adaptive Design	No
Study Stop Rules	Not stated	

[figure not shown]

[figure not shown]
Approval Date: 12-Feb-2021 17:35:16 (GMT)

[figure not shown]
Approval Date: 12-Feb-2021 17:35:16 (GMT)

[figure not shown]
Approval Date: 12-Feb-2021 17:35:16 (GMT)

[figure not shown]
Approval Date: 12-Feb-2021 17:35:16 (GMT)

[figure not shown]

2.1 List of Tables

Table 11.2-1. Criteria for Potentially Clinically Significant Laboratory Tests 21
Table 15.1.1-1 Analysis Week Windows for Efficacy Analysis 26

3.0 **List of Abbreviations**

AE	adverse event
ALT	alanine aminotransferase
ALP	alkaline phosphatase
AST	aspartate aminotransferase
ATC	Anatomical/Therapeutic/Chemical
CDC	Center for Disease Control

CFB	change from baseline
DG	diabetic gastroparesis
DGSSD	Diabetic Gastroparesis Symptom Severity Diary
DGSSS	Diabetic Gastroparesis Symptom Severity Score
eCRF	electronic case report form
ECG	electrocardiogram, electrocardiographic
EOS	end of study

GEBT	gastric emptying breath test
HbA1c	glycosylated hemoglobin A1c

ITT	intent to treat
-----	-----------------

PCS	potentially clinically significant
-----	------------------------------------

PT	Preferred Term
QTc	QT interval corrected for heart rate
QTcB	QT interval corrected for heart rate using the Bazett formula ($QTcB = QT/(RR)^{1/2}$)
QTcF	QT interval corrected for heart rate using the Fridericia formula ($QTcF = QT/(RR)^{1/3}$)
RM	rescue medication
RLM	Relamorelin
SAE	serious adverse event
SI	Le Système International d'Unités (International System of Units)
SoA	Schedule of activities
SOC	system organ class
T1DM	type I diabetes mellitus
TBL	total bilirubin
TEAE	treatment-emergent adverse event

TESAE treatment-emergent serious adverse event
WOCBP women of childbearing potential

4.0 Introduction

The statistical analysis plan (SAP) provides a more technical and detailed elaboration of the statistical analyses of the efficacy and safety data as outlined and specified in the protocol RLM-MD-04, Amendment 3 (dated 29 Apr 2019).

However, the study was early/prematurely terminated on 04 September 2020 and only an abbreviated study report will be applied to this study to report only some safety analyses and along with some basic trial characteristics data summaries.

This SAP amendment is based on the SAP dated 28 September 2020. The major change to the SAP is to add descriptive analyses for the key efficacy endpoints for the results posting on ClinicalTrials.gov and EudraCT (European Union Drug Regulating Authorities Clinical Trials Database) and add the COVID-19 data listing.

4.1 Study Design

Overall Study Design:

- Global, multicenter, randomized, double-blind, placebo-controlled, parallel-group
- Treatment Group: Relamorelin 10 µg or placebo subcutaneously twice daily
- Study Duration: 52-week Double-blind Treatment Period
- Participants who meet study entry and randomization criteria will be randomized in a 2:1 ratio to blinded treatment with relamorelin 10 µg or placebo, and will use an electronic hand-held device for reporting of their symptoms, treatment satisfaction, compliance, and use of rescue medication.

Planned enrollment for this study is 600 participants assigned to study treatment (400 to relamorelin and 200 to placebo). A total of 300 participants are expected to complete the study (200 relamorelin- and 100 placebo-treated participants).

Two different groups of participants may enter into the study, rollover participants and de novo participants.

1. Rollover participants are those who met all Screening and Run-in Period criteria in lead-in Study RLM-MD-01 or lead-in Study RLM-MD-02 (including compliance with dosing and data entry into the Diabetic Gastroparesis Symptom Severity Diary (DGSSD) during the lead-in study Run-in Period), but were not randomization-eligible at the end of the lead-in study Run-in Period. They are eligible for randomization in Study RLM-MD-04 if:
 - They had no vomiting episodes recorded in the DGSSD and had an average daily Diabetic Gastroparesis Symptom Severity Score (DGSSS) ≥ 12 at the end of the lead-in study Run-in Period.

OR

- They had vomiting episodes recorded in the DGSSD but had an average daily DGSSS of ≥ 12 and < 16 at the end of the lead-in study Run-in Period.

Rollover participants will enter the study at Visit 1 (Randomization); they will not undergo Screening (Visit -2) or Run-in Visit (Visit -1) procedures.

De novo participants are those who undergo screening and Run-in procedures in Study RLM-MD-04. De novo participants are eligible for randomization if they meet all Screening and Run-in Period criteria for Study RLM-MD-04, including:

[figure not shown]
At the Screening Visit (Visit -2):

- Male or female aged 18 years and older;
- T1DM or T2DM with controlled and stable blood glucose levels and HbA1c $\leq 11\%$;
- Symptoms suggestive of DG for at least 3 months (one of which must be nausea), with mechanical obstruction of the gastrointestinal tract as the cause of symptoms having been ruled out;
- History of nausea and/or at most a single episode of vomiting in the 2 weeks prior to Screening (Visit -2), as ascertained by participant history

[figure not shown]
At the End of the Run-in Period:

[figure not shown]
- Evidence of compliance during the Run-in Period with both the use of the electronic hand-held device for entry of data and with twice daily SC injections of the study treatment;
- No treatment with GI promotility agents during the Run-in Period;
- A score of ≥ 12 for the average of the daily DGSSS measured during the Run-in Period.

[figure not shown]
Study Schematic:

[figure not shown]

Schedule of Activities (SoA)

5.0 Objectives

Key Objectives	Key Endpoints

 • To compare the efficacy of relamorelin with that of placebo in participants with DG with respect to a composite of the following core signs and symptoms of DG: 
 ○ Nausea ○ Abdominal pain ○ Postprandial fullness ○ Bloating • To compare the safety of relamorelin with that of placebo in participants with DG 	
 • Change from baseline to Week 12 in the weekly DGSSS • Change from baseline to Week 52 in weekly average DGSSS • AEs, clinical laboratory values, vital signs, ECGs, HbA1c, and anti-relamorelin antibodies
Other Objectives	Other Endpoints

 • To assess relamorelin treatment effect on individual symptoms of DG such as nausea, abdominal pain, bloating, postprandial fullness, early satiety, and vomiting frequency 	
 • Change from baseline to Week 12 and Week 52 in the following: 
 ○ Nausea ○ Abdominal pain ○ Bloating ○ Postprandial fullness ○ Early satiety ○ Vomiting frequency

6.0 Populations for Analyses

6.1 Screened Population

The Screened Population will consist of all participants who sign informed consent.

6.2 Intent-to-Treat Population

The Intent-to-Treat (ITT) Population will consist of all randomized participants.

6.3 Modified Intent-to-Treat Population

The Modified Intent-to-Treat (mITT) Population will consist of all randomized participants with ≥ 1 postbaseline assessment of DGSSD. It is a subset of the ITT Population.

6.4 Safety Population

The Safety Population will consist of all participants who receive ≥ 1 administration of study treatment.

The Safety Population will be used for all safety analyses. Participants will be analyzed according to the treatment they actually received during the Double-blind Treatment Period. In case a participant receives relamorelin 10 μg and placebo alternatively during the study, the participant will be included in the relamorelin 10 μg group for purpose of safety analyses.

7.0 **Participant Disposition**

The number and percentage of participants screened will be tabulated by de novo participants and rollover participants from lead-in studies RLM-MD-01 and RLM-MD-02 for the Screened Population.

The number and percentage of participants who complete the study and of participants who prematurely discontinue will be presented by treatment group and overall for the ITT Population. All participants who prematurely discontinue will be listed by discontinuation reason.

The number and percentage with significant protocol deviations will be presented by treatment group and overall for the ITT Population.

8.0 **Demographics and Other Baseline Characteristics**

Demographic parameters (e.g., age, age group, race, ethnicity, sex, geographic region) will be summarized by treatment group and overall for the Safety Population.

Abnormalities in participants' medical and surgical histories will be coded using the *Medical Dictionary for Regulatory Activities*, version 23.0 or newer. A data listing for medical and surgical histories will be presented.

Prior medication is defined as any medication started before the date of the first dose of double-blind study treatment. *Concomitant medication* is defined as any medication taken on or after the date of the first dose of double-blind study treatment.

The *WHO Drug Dictionary*, Version B2 March 2017 or newer, will be used to classify prior and concomitant medications by WHO Drug Anatomical/Therapeutic/Chemical (ATC) category and drug preferred name. A data listing for prior and concomitant medications will be presented.

9.0 **Extent of Exposure**

A listing of the investigational product dosing records will be provided for ITT population.

10.0 **Efficacy Analyses**

The main efficacy assessment is the Diabetic Gastroparesis Symptom Severity Diary (DGSSD), a 7-item, patient-reported daily diary designed to assess the severity of 6 core signs and symptoms of DG—nausea, abdominal pain, postprandial fullness, bloating, vomiting, and early satiety—and the frequency of vomiting episodes. The severity of DG symptoms are assessed using a 0 to 10 numerical rating scale (NRS), on which 0 = “no” or “not at all uncomfortable” (ie, absence of the DG symptom) and 10 = “worst possible” or “most uncomfortable” (ie, worst experience of the DG symptom).

The Diabetic Gastroparesis Symptom Severity Score (DGSSS) is an overall assessment of the severity of non-vomiting symptoms. It is the sum of the four individual DGSSD items of nausea, abdominal pain, postprandial fullness and bloating. The score ranges from 0 to 40.

Participants report their symptoms daily from Visit 1/Baseline to Visit 4/Week 12, and for each of the 4 weeks preceding Visits 5/Week 24, Visit 6/Week 36, and Visit 7/Week 52 in the DGSSD.

Baseline values for DGSSD based parameters are derived from the DGSSD assessment collected during the Run-in Period as the average of the two weekly values of Week -2 and Week -1.

There are two key efficacy endpoints as follows:

Key Endpoints	Description	Timing
CFB to Week 12 in weekly DGSSS	Change from baseline to Week 12 in weekly DGSSS	Week 12
CFB to Week 52 in weekly average DGSSS	Change from baseline in average of the weekly average DGSSS from Weeks 49 to 52	Week 49-Week 52

Since the study was early terminated, only descriptive analyses for the key efficacy endpoints will be performed.

11.0 **Safety Analyses**

The safety analysis will be performed using the Safety Population. The safety parameters will include adverse events (AEs), clinical laboratory, electrocardiogram, vital sign parameters.

11.1 **Adverse Events**

All AEs and serious AEs (SAEs) will be collected from the signing of the informed consent form (ICF) until 30 days after the final visit in the study (Visit 7) or Early Termination Visit at the time points specified in the SoA. For rollover participants, ongoing AEs from lead-in Studies RLM-MD-01 and RLM-MD-02, and new AEs that occur after the signing of the ICF for RLM-MD-04 are considered to be AEs in RLM-MD-04.

Adverse events will be coded by system organ class and preferred term using the *Medical Dictionary for Regulatory Activities (MedDRA)*, version 23.0 or newer.

An AE will be considered a treatment-emergent adverse event (TEAE) if the AE began or worsened (increased in severity or became serious) on or after the date of the first dose of double-blind study intervention. However, an AE that occurs more than 30 days after the last dose of study intervention will not be counted as a TEAE. Per case report form instructions, a new AE record will be created with a new AE onset date for any AE that worsens. Therefore, TEAEs can simply be identified as those AEs with recorded onset date on or after the date of the first dose of double-blind study intervention and within 30 days of the last dose of double-blind study intervention.

An AE will be considered a treatment-emergent SAE (TESAE) if it is a TEAE that also is an SAE.

The number and percentage of participants with TEAEs, death, TESAE, treatment related TEAE, TEAEs leading to treatment discontinuation, and TEAEs leading to discontinuation from study will be presented by treatment group.

The number and percentage of participants reporting TEAEs in each treatment group will be tabulated by descending percentage in Relamorelin group, by system organ class (SOC), preferred term, and severity. If more than 1 AE is coded to the same preferred term for the same participant, the participant will be counted only once for that preferred term using the greatest severity for the summarization by severity.

The number and percentage of participants reporting treatment-related TEAE, TESAEs, treatment related TESAE, and having TEAEs leading to discontinuation of the study in each treatment group will be summarized by system organ class and preferred term.

In addition, listings for participants who died, participants with AEs, participants with TESAEs, participants with TEAEs leading to discontinuation from study will be presented.

11.2 Clinical Laboratory Parameters

Clinical laboratory test values from all assessments (including those from unscheduled or repeat assessments) will be considered potentially clinically significant (PCS) if they meet either the lower-limit or higher-limit PCS criteria listed in [Table 11.2-1](#).

The number and percentage of participants who have PCS post-baseline clinical laboratory values will be tabulated by treatment group for the Double-blind Treatment Period. The percentages will be calculated relative to the number of participants with available non-PCS baseline values and at least 1 post-baseline assessment for the Double-blind Treatment Period. The numerator will be the total number of participants with available non-PCS baseline values and at least 1 PCS post-baseline value for the Double-blind Treatment Period.

[figure not shown]

Table 11.2–1. Criteria for Potentially Clinically Significant Laboratory Tests

Parameter	SI Unit	Lower Limit	Higher Limit
CHEMISTRY			
Albumin	g/L	< 0.9 * LLN	> 1.1 * ULN
Alanine Aminotransferase (ALT)	U/L	—	≥ 3 * ULN
Alkaline Phosphatase	U/L	—	≥ 3 * ULN
Aspartate Aminotransferase (AST)	U/L	—	≥ 3 * ULN
Calcium	mmol/L	< 0.9 * LLN	> 1.1 * ULN
Chloride	mmol/L	< 0.9 * LLN	> 1.1 * ULN
Cholesterol	mmol/L	—	> 1.6 * ULN
Creatinine	μmol/L	—	> 1.3 * ULN
Potassium	mmol/L	< 0.9 * LLN	> 2.0 * ULN
Glucose, Fasting	mmol/L	< 0.9 * LLN	> 2.5 * ULN
Glycohemoglobin A1C	%		Increase of ≥ 0.5%
Glycohemoglobin A1C	%		Increase of ≥ 1%
Sodium	mmol/L	< 0.9 * LLN	> 1.1 * ULN
Total Bilirubin	μmol/L	—	> 1.5 * ULN
Total Protein	g/L	< 0.9 * LLN	> 1.1 * ULN
Triglycerides, Fasting	mmol/L	—	≥ 3 * ULN
Urea (BUN)	mmol/L	—	> 1.2 * ULN
Magnesium	mmol/L	< 0.9 * LLN	> 1.1 * ULN
Bicarbonate	mmol/L	< 0.9 * LLN	> 1.1 * ULN
Phosphate	mmol/L	< 0.9 * LLN	> 1.1 * ULN
Uric Acid	μmol/L	< 0.9 * LLN	> 1.1 * ULN
HEMATOLOGY			
Basophils Absolute Cell Count	10 ⁹ /L	—	> 3 * ULN
Eosinophils Absolute Cell Count	10 ⁹ /L	—	> 3 * ULN
Hematocrit	Ratio	< 0.9 * LLN	> 1.1 * ULN
Hemoglobin	g/L	< 0.9 * LLN	> 1.1 * ULN
Lymphocytes Absolute Cell Count	10 ⁹ /L	< 0.8 * LLN	> 1.5 * ULN
MCH	PG	—	> 3 * ULN
MCHC	G/L	—	> 3 * ULN
MCV	fL	< 0.9 * LLN	> 1.1 * ULN
Monocytes Absolute Cell Count	10 ⁹ /L	—	> 3 * ULN
Neutrophils Absolute Cell Count	10 ⁹ /L	< 0.8 * LLN	> 1.5 * ULN
Platelet Count	10 ⁹ /L	< 0.5 * LLN	> 1.5 * ULN

Table 11.2–1. Criteria for Potentially Clinically Significant Laboratory Tests

Parameter	SI Unit	Lower Limit	Higher Limit
Red Blood Cell Count (Erythrocyte Count)	10 ¹² /L	< 0.9 * LLN	> 1.1 * ULN
White Blood Cell Count	10 ⁹ /L	< 0.7 * LLN	> 1.5 * ULN
URINALYSIS			
pH		< 0.9 * LLN	> 1.1 * ULN
Specific Gravity		—	> 1.1 * ULN

LLN: Lower limit of normal value provided by the laboratory.

ULN: Upper limit of normal value provided by the laboratory.

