9.4.4 Clinical Safety Laboratory Assessments

- See [Appendix 2](#) for the list of clinical laboratory tests to be performed and refer to the SoA for the timing and frequency.
- The investigator must review the laboratory report, document this review, and record any clinically relevant changes occurring during the study in the AE section of the eCRF. The laboratory reports must be filed with the source documents. Clinically significant abnormal laboratory findings are those which are not associated with the underlying disease, unless judged by the investigator to be more severe than expected for the participant's condition.
- All laboratory tests with values considered clinically significantly abnormal during participation in the study or within 30 days after the last dose of study treatment should be repeated until the values return to normal or baseline, or are no longer considered clinically significant by the investigator or MSP.
 - If such values do not return to normal/baseline within a period of time judged reasonable by the investigator, the etiology should be identified and the sponsor notified.
 - All protocol-required laboratory assessments, as defined in [Appendix 2](#), must be conducted in accordance with the laboratory manual and the schedule of activities.
 - If laboratory values from non-protocol specified laboratory assessments performed at the institution's local laboratory require a change in participant management or are considered clinically significant by the investigator (eg, SAE or AE or dose modification), then the results must be recorded in the eCRF.

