15.4 Repeated or Unscheduled Assessments of Safety Parameters

If a participant has repeated assessments before the start of double-blind treatment with investigational product, the results from the final assessment made before the date of the first dose will be used as baseline.

However, all post-baseline assessments will be used for PCS value determination, and all assessments will be presented in the data listings.

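### SAP Table 11.2-1 flags high potassium only above 2.0 × ULN, so the by-arm laboratory table cannot show high potassium; the MCH, MCHC and specific gravity rows are also inert

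*SAP*

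**What the plan says.** SAP Section 11.2 states that laboratory values from all assessments, including unscheduled and repeat ones, "will be considered potentially clinically significant (PCS) if they meet either the lower-limit or higher-limit PCS criteria listed in" its table of criteria (Table 11.2-1). What comes out is a count by arm: "The number and percentage of participants who have PCS post-baseline clinical laboratory values will be tabulated by treatment group". Baseline status restricts who can be counted: "The numerator will be the total number of participants with available non-PCS baseline values and at least 1 PCS post-baseline value". Both statements refer to the double-blind period.

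The potassium row of the table reads "Potassium mmol/L < 0.9 * LLN > 2.0 * ULN". Sodium, chloride, calcium, magnesium, bicarbonate and phosphate all have > 1.1 × ULN as the high limit. MCH and MCHC have > 3 × ULN and no low limit; urine specific gravity has > 1.1 × ULN and no low limit. The footnote leaves the reference limits to the laboratory ("ULN: Upper limit of normal value provided by the laboratory"), so the SAP prints no value in mmol/L.

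Two other places bear on the point. SAP Section 15.4 says that "all post-baseline assessments will be used for PCS value determination, and all assessments will be presented in the data listings". Protocol Section 9.4.4 requires the investigator to "record any clinically relevant changes occurring during the study in the AE section of the eCRF".

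**The concern.** A PCS table counts abnormal values by arm with a fixed rule, independent of investigator judgment. It can do so only if the limit lies where real values can fall. A potassium limit at twice the ULN does not, so the high side is switched off while the low side still works. If the table shows a single potassium line without direction, which Section 11.2 does not rule out, its counts will reflect low potassium alone.

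Protocol Section 10.3.3 foresees laboratory data summarized as appropriate, with descriptive statistics and shift tables as examples. In the abbreviated SAP the PCS table is the only by-arm laboratory summary that can be seen. A reader who finds about 0% on both arms could take a limit that cannot fire as evidence of no difference.

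Potassium is not a trivial analyte here: exclusion criterion 18 in Protocol Section 6.2.3 lets de novo participants enter with an eGFR as low as 30 mL/min. The corresponding rule for rollover participants is not visible.

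**Working it through.** **Inputs.** The multipliers come from SAP Table 11.2-1. The reference limits are not in the documents and are assumed: potassium ULN 4.8-5.5 and LLN 3.3-3.6 mmol/L; MCH ULN 32-35 pg; MCHC ULN 350-370 g/L; specific gravity ULN 1.025-1.035. The plan states no mmol/L limit and no expected rate, so there is no figure of its own to reproduce.

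**Step 1: the limits.** Limit = multiplier × reference limit.

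| Row | Calculation | Limit |
|---|---|---|
| Potassium, high, as written | 2.0 × 4.8 to 2.0 × 5.5 | 9.6-11.0 mmol/L |
| Potassium, high, at 1.1 | 1.1 × 4.8 to 1.1 × 5.5 | 5.28-6.05 mmol/L |
| Potassium, low, as written | 0.9 × 3.3 to 0.9 × 3.6 | 2.97-3.24 mmol/L |
| MCH | 3 × 32 to 3 × 35 | 96-105 pg |
| MCHC | 3 × 350 to 3 × 370 | 1050-1110 g/L |
| Specific gravity | 1.1 × 1.025 to 1.1 × 1.035 | 1.128-1.139 |

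Two of these hardly depend on the assumption. Any MCHC ULN of 334 g/L or more puts the limit above 1000 g/L (3 × 334 = 1002). Any specific gravity ULN of at least 1.000 puts the limit at 1.10 or more.

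**Step 2: can a potassium value reach the limit?** As an illustration, take potassium as log-normal with assumed mean/SD of 4.3/0.4, 4.5/0.5 or 4.8/0.6 mmol/L. Then s² = ln(1 + (SD/mean)²), m = ln(mean) − s²/2, z = (ln(limit) − m)/s, and the share above the limit is 1 − Φ(z).

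The combination most favourable to the plan is mean 4.8, SD 0.6, ULN 4.8:

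- s² = ln(1 + 0.015625) = 0.0155, so s = 0.1245, and m = 1.5609.
- At 2.0 × ULN: z = (ln 9.6 − 1.5609)/0.1245 = 5.6; share about 9 × 10⁻⁹ per value.
- At 1.1 × ULN: z = (ln 5.28 − 1.5609)/0.1245 = 0.83; share about 20%.

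At the other end (mean 4.3, SD 0.4, ULN 5.5), z is 10.2 for 2.0 × ULN and the share at 1.1 × ULN is about 0.01%. So the limit as written yields no counts under any of these assumptions, while a 1.1 limit can yield some.

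**Step 3: is potassium out of line with the rest of the table?** Rows with < 0.9 × LLN: albumin, calcium, chloride, potassium, fasting glucose, sodium, total protein, magnesium, bicarbonate, phosphate, uric acid, hematocrit, hemoglobin, MCV, red cell count and urine pH, 16 in all. Fourteen pair it with > 1.1 × ULN. The exceptions are fasting glucose (2.5) and potassium (2.0). A wide glucose limit is understandable in a diabetic population; the SAP gives no reason for potassium. Magnesium is not among the protocol's laboratory tests (Table 12-1), so five of the six comparator rows named above are protocol tests.

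**Step 4: what the table would show.** At the planned size (400 relamorelin, 200 placebo; the number after early termination is not given), the high side would read 0/400 and 0/200. The usual one-sided 95% upper bounds would be 1 − 0.05^(1/400) = 0.75% and 1 − 0.05^(1/200) = 1.5%, and neither would mean anything, because the rule cannot register an event. If clinically high potassium truly occurred in 3% against 1%, then 400 × 0.03 = 12 and 200 × 0.01 = 2 participants would go uncounted as PCS.

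**The case against.** The case on the other side is mainly about weight.

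- **The stakes are modest.** The study was stopped early and the SAP is an abbreviated plan (SAP Sections 4.0 and 16.0). No endpoint or decision rule uses the potassium count, potassium is not an adverse event of special interest, and Protocol Section 3.2 reports no relevant Phase 2b abnormality outside glycemic measures. This stands, and it limits the point to a gap in detection. It does not remove it: the abbreviated report is mainly a safety report, and this table was kept in it.
- **High values are visible elsewhere.** All values are listed, and changes the investigator finds clinically relevant become adverse events, which SAP Section 11.1 tabulates by arm. True, so the values are uncounted only as PCS. But no incidence by arm is planned from the listings, and the adverse event route depends on the judgment that a PCS rule is meant to bypass.
- **The 1.1 multiplier is a pattern in the table, not a stated rule.** It also does not give equal stringency across analytes. For an assumed sodium ULN of 145 mmol/L and mean/SD of 140/3, 1.1 × ULN = 159.5, which is (159.5 − 140)/3 = 6.5 SD out. This stands. The pattern shows that potassium is out of line, not that 1.1 was intended, so the sponsor should be free to justify another attainable limit.
- **A 1.1 limit could be noisy.** The share of single values above it runs from about 0.01% to 20% in Step 2, and any one post-baseline value counts. The 20% needs a population mean equal to the ULN, but the range is a fair reason to choose the limit with care.
- **Artefacts could trip the limits.** A hemolysed or agglutinated sample might. The conclusion is about genuine results.

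**Conclusion.** The point holds and should be corrected. As written, the high side of the potassium row will return about 0% on both arms and cannot show a difference. Values from 5.28-6.05 mmol/L up to 9.6-11.0 mmol/L, which the multiplier used for the other electrolytes would flag, are left out of the PCS count. The mmol/L figures rest on an assumed ULN of 4.8-5.5, but no plausible ULN makes twice its value a usable reporting limit. The low side is attainable, so the row as a whole need not read zero.

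The MCH, MCHC and specific gravity rows carry no information. That is a lesser matter, because hemoglobin, hematocrit, red cell count and MCV have working limits. No efficacy endpoint or test is affected.

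**What to change.** In SAP Table 11.2-1:

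1. Change the high potassium limit to > 1.1 × ULN, as for the other electrolytes, or to another attainable limit with a one-line justification in the SAP. Check the present 2.0 against the source of the criteria.
2. Give MCH and MCHC the MCV limits (< 0.9 × LLN, > 1.1 × ULN), or drop the two rows.
3. Drop the specific gravity row or give it an attainable limit.
4. Run the PCS table with the corrected limits, or rerun it if it has already been produced.

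The cost is an edit to one SAP table and one run of a programmed output. The downside is more flagged potassium values to describe; how many depends on the laboratory's ULN and the limit chosen. These are reporting limits only, and no rule for managing participants changes.
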